We hypothesize that patient specific and sleep-specific factors influence nocturnal lipolysis. Patient factors may include age, sex, or body mass index (BMI). Sleep-specific factors may include OSA severity and/or OSA-induced sympathetic activation, elapsed time, or sleep stage. Additional outcomes of interest are effects of OSA, CPAP on circulating genetic/epigenetic changes.

3. Background (briefly describe pre-clinical and clinical data, current experience with procedures, drug or device, and any other relevant information to justify the research)

OSA induces repetitive upper airway closure during sleep, and affects 24% of middle aged men and 9% of women in the United States[3]. Several studies suggest that OSA may induce cardio-metabolic complications such as insulin resistance, endothelial dysfunction, and dyslipidemia[4] culminating in cardiovascular disease and death[5]. Unfortunately, it remains unclear what mediates detrimental outcomes in OSA. We have shown that OSA causes rapid FFA elevations during sleep in heart failure subjects, which can be prevented by supplemental oxygen [1]. We speculate that stimulation of the sympathetic nervous system by OSA and intermittent hypoxia cause lipolysis, leading to excessive FFA mobilization from adipose tissue.

It is not known whether OSA causes surges of FFA in non-CHF patients, and whether CPAP can abolish the increase. It is also unclear which patient-related or sleep apnea features predict nocturnal FFA elevations, and

whether FFA elevations from OSA are associated acutely with detrimental physiologic changes. In subjects with a history of OSA, we will examine nocturnal FFA in the presence or absence of therapeutic CPAP. We hypothesize that CPAP withdrawal leads to increases in nocturnal FFA. We will also determine whether morning endothelial function and glucose tolerance correlate with nocturnal FFA changes.

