PSG setup. On each study night from 22:40 until 06:40, a PSG will be performed. The sleep study will include electroencephalography, electrooculography, oxygenation, respiratory effort, CPAP airflow, and transcutaneous CO₂ monitoring. Respiratory effort will be measured by thoraco-abdominal movement assessed by mercury strain gauges. Surface electrodes will be placed at C₃A₂ and C₃O₁, a submental electrode, and left and right electro-oculogram will be used to stage sleep. Electrocardiograph (EKG) tracings will be recorded from three chest electrodes. Continuous measurement of oxygen saturation will be recorded using an ear oximeter (model No 472-1A, Hewlett Packard, Waltham, Mass). Transcutaneous CO₂ will be monitored using a Radiometer TCM-4 device. Signals from the electroencephalograph, EKG, electromyogram, electrooculogram, respiratory strain gauge, ear oximeter and thermistors will be recorded on a computer with RemLogic software.

During the CPAP night, patients will sleep using CPAP set to their prescribed home CPAP settings. Airflow will be recorded with a pneumotachograph in the CPAP circuit. CPAP pressure will be titrated if necessary to prevent

obstructive hypopneas and apneas. During NDS nights, ClearPassage® strips will be applied at bedtime. Flow will be measured using a nasal cannula and oral thermistor.

[figure not shown]
Blood work and urine collection

All samples will be obtained via the indwelling IV, without awakening the subject. Blood samples will be drawn at 30 to 60 minute intervals beginning at 5:30 PM and continuing until the next morning at 6:30 AM as shown in the figure below. At 10:30 PM, when the sleep study starts, blood is sampled at 30 minute intervals in order to capture dynamic changes in FFA metabolism during sleep. Each blood sample will be 4 cc in volume and placed into lavender top tubes (EDTA) for centrifugation to obtain plasma. Cells are removed from plasma by centrifugation for 10 minutes at 1500 x using a refrigerated centrifuge. If necessary, based on nursing schedules, the timing of sampling and sleep procedures can be shifted up to 1 hour later or earlier.

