Dual-energy X-ray absorptiometry (DEXA). After the baseline glucose level for the OGTT has been drawn and the patient has consumed the glucose solution, they will undergo a DEXA scan. The DEXA scan will be used to estimate fat mass, which will be one of the variables analyzed as a predictor of FFA elevation.

Subjects may eat breakfast after the OGTT testing is completed

To minimize the impact of sleep loss on driving safety, subjects are asked to either (1) arrange for an alternate means of transportation home (this is mentioned on the consent or to (2) sleep as needed for up to 4 additional hours before discharge.

Repeat sleep testing:

Repeat sleep tests may be requested from the subject under the following circumstances:

- (1) A technical problem with data acquisition including PSG lead failure/artifacts, incomplete blood collection from IV insertion or maintenance problems.
- (2) Poor sleep efficiency <50% of time in bed

If the initial sleep study meets these criteria and a repeat test is deemed necessary by the PI, then the repeat testing will be scheduled at least 1 week following the initial study.

Scoring. Sleep will be scored according to Rechtschaffen and Kales criteria. Respiratory events will be scored according to AASM criteria. Apneas will be considered present when there is no air flow for >10 seconds. Obstructive apneas will be considered present when apneas are associated with positive strain gauge deflections indicating thoracic movement. Apneas will be considered central in origin when cessation of air flow is not accompanied by thoracic movement as measured by the strain gauge. Mixed apneas will be defined by episodes of no air movement resulting from central apnea followed by obstruction. Hypopneas will be scored for reductions in airflow of 30% lasting >10 seconds accompanied by either an arousal or fall in oxyhemoglobin saturation of 3% or greater.

Data Analysis and Anticipated Outcomes:

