The primary outcomes is nocturnal plasma FFA levels. The main independent variable is OSA versus CPAP exposure during sleep. Since FFA are measured multiple times per subject per night, we will perform mixed linear model analysis using condition as a fixed factor and subject ID as a random factor. Sleep physiology that is measured on a continuous basis will be condensed into 30 minute bins to create a parallel data structure with metabolic parameters. As a secondary analysis, we will also examine whether there are patient-specific (“static”) determinants of FFA level during sleep such as age, sex, or body mass index and whether these variables interact with sleep (“dynamic”) variables such as OSA severity. We hypothesize that OSA exposure increases FFA, compared to CPAP. We will then examine whether sleep physiology (e.g. AHI, arousals, heart rate) is dynamically associated with FFA, and whether urine catecholamine levels are associated with increases in FFA. For variables measured once (RHI, morning lipid profile) or averaged (e.g. nocturnal FFA level) we will perform one-way ANOVA for comparisons. We will also compare sleep physiology between the 3 nights, examining variables such as apnea hypopnea index, metrics of hypoxia, and sleep architecture/duration. Data analysis will be performed with a biostatistician and described under the “Study Statistics” section.

b. Study duration and number of study visits required of research participants.

Each study subject will make two overnight visits to the sleep lab. Subjects will be screened with an initial telephone interview. During this screening, only information necessary to assess eligibility for the study will be collected, or information voluntarily provided by the patient to initiate or maintain correspondence. Subjects without any of the self-reported exclusionary criteria will be scheduled for a face-to-face visit for further screening. At this visit, eligibility for

participation in the study protocols will be confirmed. Urine screening for pregnancy in women of child-bearing age will also be performed.

c. Blinding, including justification for blinding or not blinding the trial, if applicable.

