We will include adults of all races ≥ 20 and ≤ 75 years old, with a history of mild to severe OSA (AHI or RDI > 10). They must also own a CPAP machine and report the ability to tolerate sleeping with or without CPAP during the night.

Exclusion Criteria:

1. Uncontrolled hypertension with systolic blood pressure > 170 or diastolic blood pressure > 110
2. Congestive heart failure
3. Use of, clonidine, or nicotinic acid medication
4. Diabetes requiring the use of insulin
5. Pregnancy, by urine testing in women of child-bearing age

6. Patients with a prior history of falling asleep while driving, involved in a near-miss or motor vehicle accident, or and those in high-risk occupations such as commercial drivers or pilots.
7. Hemoglobin < 10 g/dL on point of care screening.

6. Drugs/ Substances/ Devices

- a. The rationale for choosing the drug and dose or for choosing the device to be used.

During CPAP withdrawal nights (both at home and in the lab) we will use NDS as a CPAP placebo. NDS may improve snoring but have no treatment value for OSA[6]. By including NDS as a placebo, we will avoid potential confounding such as anxiety caused by stopping CPAP.

- b. Justification and safety information if non-FDA approved drugs without an IND will be administered.
N/A

Study Statistics

The overall analysis plan has been presented in section 4, “Data Analysis and Anticipated Outcomes”. In this section we briefly address the statistical methods to be used for analysis separated by specific aim:

Specific Aim 1: To examine whether OSA, elicited by CPAP withdrawal, causes lipolysis and cardio-metabolic dysfunction.

Primary outcome: FFA level, comparing between CPAP and OSA nights, analyzed using linear mixed effect models.
Independent variable: CPAP/OSA exposure.

Specific Aim 2: To examine factors associated with lipolysis during sleep.

Primary outcome: FFA level

Independent variables: OSA severity (AHI, arousal index, heart rate, urine catecholamines), Patient factors (age, sex, body mass index/fat distribution).

These analyses are primarily designed to understand the heterogeneity of lipolysis during CPAP withdrawal.

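### The primary FFA model has no night-level term although condition is applied to whole nights, so its standard error, interval and p-value for CPAP versus OSA are not calibrated, in a direction the documents do not fix

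*Combined protocol and SAP*

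**What the plan says.** Section 4a, Data Analysis and Anticipated Outcomes, makes nocturnal plasma FFA the primary outcome. Because FFA is measured repeatedly within a night, "we will perform mixed linear model analysis using condition as a fixed factor and subject ID as a random factor". It then says that "Data analysis will be performed with a biostatistician and described under the" Study Statistics section. That section refers back to 4a and, for Aim 1, adds only: "Primary outcome: FFA level, comparing between CPAP and OSA nights, analyzed using linear mixed effect models". The Aim 2 mixed models for OSA severity and sympathetic activation again give subject as the only random effect.

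Four design features bear on this:
- Section 4a, Sequence and Timing of visits: CPAP and nasal strips are each used for a complete night, in random order, more than 1 week and at most 3 months apart.
- Section 4a, Blood work and urine collection: from 22:30 "blood is sampled at 30 minute intervals in order to capture dynamic changes in FFA metabolism during sleep", ending at 06:30. Also, "the timing of sampling and sleep procedures can be shifted up to 1 hour later or earlier".
- Section 4a, Repeat sleep testing: a failed or poor-sleep night may be redone, and "the repeat testing will be scheduled at least 1 week following the initial study". Which nights are then analysed is not stated.
- Section 2, Aim 2: "Sleep-specific factors may include OSA severity and/or OSA-induced sympathetic activation, elapsed time, or sleep stage". Elapsed time is thus a candidate influence on FFA, yet the primary model has no time term.

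Section 4a also plans a one-way ANOVA for averaged quantities, with nocturnal FFA as an example. It mentions no pairing by subject.

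**The concern.** The contrast of interest varies only between a subject's two nights. A model with a subject intercept alone treats the roughly 34 samples per subject as exchangeable, as if each were a separate piece of evidence about condition. Anything shared by one night's samples (that night's meal, sleep, stress, line handling or assay conditions) or by neighbouring samples breaks that assumption and tends to make the standard error too small. An overnight FFA trend left out of the model acts the other way: it inflates the residual and can offset or reverse the error.

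This is the primary analysis. If CPAP withdrawal has no effect, the false-positive rate is not held at 5%. If it has an effect that differs between people, the confidence interval is wrong. Such differences are expected, since Study Statistics says of Aim 2 that "These analyses are primarily designed to understand the heterogeneity of lipolysis during CPAP withdrawal".

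**Working it through.** **The plan's own figure.** Sample Size gives ΔFFA of 0.047 in men and 0.021 in women, SD 0.04 mmol/l. Then d = (0.047 − 0.021)/0.04 = 0.65. A two-sided t-test at 5% and 80% power needs 38.14 per sex, so 39 each and 78 in all; 78/0.85 = 91.8, so 92. Both figures reproduce. They concern the sex difference; no standard error or power is given for CPAP versus OSA.

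**Inputs.** n = 78; 2 nights; m = 8 h/0.5 h + 1 = 17 samples per night. *Assumed*: SD_diff = 0.04 mmol/l is the SD of the difference between a subject's two night means; within-night SD σ is 0.04 to 0.10; drift D is a straight-line change over the night, the same on both nights. Sample Size does not say what the 0.04 measures, and section 4a mentions an earlier within-night withdrawal study.

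**Formulas (balanced data).**
- True SE = SD_diff/√n = 0.04/√78 = 0.0045.
- Night variance = SD_diff²/2 − σ²/17.
- Residual variance that the model pools: s² = [2(m − 1)σ² + 2m(0.09375 D²) + (m/2)SD_diff²]/(2m − 1). Here 0.09375 D² is the variance of 17 equally spaced points on a line rising by D.
- Model SE = √(2s²/(nm)).
- Type I error = 2Φ(−1.96 × model SE/true SE).

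**One cell in full (σ = 0.06).** Without drift, s² = (32 × 0.0036 + 8.5 × 0.0016)/33 = 0.1288/33 = 0.003903. Model SE = √(2 × 0.003903/1326) = 0.0024; true SE/model SE = 1.87; type I error 29%. With D = 0.2, add 34 × 0.00375 = 0.1275 to the numerator: s² = 0.2563/33 = 0.007767, model SE = 0.0034, type I error 14%.

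| σ | night share of within-subject variance | no drift | D = 0.2 | D = 0.3 | drift giving full offset |
|---|---|---|---|---|---|
| 0.04 | 0.31 | 46% | 20% | 8% | 0.35 |
| 0.06 | 0.14 | 29% | 14% | 6% | 0.32 |
| 0.08 | 0.06 | 17% | 9% | 4% | 0.27 |
| 0.10 | 0.02 | 9% | 5% | 2% | 0.19 |

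**Break-even.** The two SEs agree when the total within-subject residual SD, drift included, is 0.04 × √(17/2) = 0.117 mmol/l. Below that the model SE is too small; above it, too large.

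**If 0.04 is the wrong anchor.** For SD_diff of 0.03 and 0.06 the break-even is 0.087 and 0.175. Without drift, type I error is 34% down to 7% for 0.03 (σ 0.04 to 0.08) and 58% down to 25% for 0.06 (σ 0.04 to 0.10). At 0.2 drift it is 9% down to 2%, and 37% down to 18%.

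**Serial correlation alone.** With no night variance and no drift, a within-night AR(1) correlation of 0.5 gives 25%.

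**Simulation (3,000 null trials per setting; σ = 0.04, 0.08, 0.10).** The subject-only model rejected 45/16/9% without drift, 20/9/5% at 0.2 and 8/4/2% at 0.3. A night effect plus time rejected 4.5 to 5.3%, as did a paired test of night means. With AR(1) correlation of 0.6 in the data and no serial term, night effect plus time still rejected 4.7 to 5.4%.

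**Time without night.** Adding time alone removes the offset: at 0.3 drift, 8% down to 2% becomes 46% down to 9%.

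**Interval.** Take a true mean effect of (0.047 + 0.021)/2 = 0.034, no night-to-night variation, and only subject-specific response. The nominal 95% interval then covers 53 to 90% without drift and 80 to 95% at 0.2; with night effect and time, 95 to 96%.

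**Aim 2.** CPAP is set to prevent obstructive events, so binned AHI should be low throughout one night and high on the other. Assume AHI of about 2 on CPAP and, off CPAP, mean 35, between-subject SD 15 and bin SD 10 to 30. A null subject-only model of FFA on binned AHI rejected about 34 to 43% at σ = 0.04, falling to 7 to 8% at 0.10, without drift. At 0.2 drift it rejected about 13 to 19%, falling to 4 to 5%. Urine catecholamines, measured once per night, gave about 46% down to 10% and 20% down to 5%.

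**The case against.** **The size is unknowable from the documents.** This stands. No variance component is reported, and the 0.04 may not be a between-night SD. A reader might infer that the standard error is certainly too small, or that a false-positive rate near 46% is established. Neither is supported: drift of 0.19 to 0.35 mmol/l would cancel the error under the assumed anchor, and more would make the test conservative. What survives is that calibration depends on quantities the plan neither models nor reports.

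**The test decision would probably not change.** Under the same anchor, 0.034/0.0045 gives z of about 7.5, and section 1 calls this a pilot study. This also stands, and it limits the practical consequence to the interval and to the case of no effect.

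**The averaged-FFA ANOVA already works at night level.** It does avoid counting same-night samples as independent, and if run unpaired on positively correlated nights it would err conservatively. But it is not the primary analysis and states no pairing, so it does not repair the primary test.

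**A biostatistician will settle the details.** The plan sends the reader to Study Statistics, which adds no term.

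**Binning protects the Aim 2 models.** A reader might infer that only once-per-night covariates are affected, since section 4a puts continuous sleep measures into 30-minute bins. It does not follow: a covariate recorded every half hour can still vary mostly between nights.

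**Conclusion.** The omission is certain from the text; its direction and size are not. As written, the primary model gives a calibrated standard error only if night-to-night variance, serial correlation and overnight trend are all absent, or if their effects happen to cancel. It is anticonservative if night-to-night or serial variation dominates, and may be neutral or conservative if there is a strong unmodelled trend. The percentages above rest on balanced data, 17 samples per night and an assumed between-night SD; they show what is possible, not what will happen.

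The point estimate and the 78/92 sample size are not in question. The main consequences are a wrong confidence interval for the primary contrast and an uncontrolled false-positive rate if there is no effect. All Aim 2 mixed models whose covariates differ mainly between nights share the fault: binned AHI, ODI and arousals as well as urine catecholamines. It should be fixed before analysis.

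**What to change.** Replace the model sentence in section 4a, and echo it in Study Statistics, with wording such as: *FFA will be modelled on condition and time within the night, with random effects for subject and for night within subject; each study night, including any repeat night that is kept, has its own identifier.* Unless repeat nights are kept, this equals a subject-by-condition random effect. Alternatively, make a paired within-subject comparison of night-mean FFA the primary test. Either is enough.

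Do not add time without the night effect. Keep the night effect in all Aim 2 mixed models of FFA, not only those with once-per-night covariates. Whether time is elapsed or clock time, and whether a serial within-night covariance is added, is optional.

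The cost is one sentence for the primary model and one for Aim 2, with no new data and no change to enrolment. The interval will usually be wider: under the 0.04 assumption, about 1.2 to 2.6 times without drift and 1.0 to 1.5 times at 0.2 drift. At 0.3 drift it is 0.85 to 1.13 times, so it could be narrower.

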- *Sex-specific effects:* This will be assessed by (1) comparing mean change in FFA level during CPAP withdrawal between men and women (unpaired T-test); (2) modeling mean FFA level as a function of sex (as well as sex x BMI interactions) in multivariable regression. We hypothesize that men will exhibit greater OSA-induced FFA elevation than women, with or without adjustment for OSA severity and fat distribution.
- *Effects of OSA severity or sympathetic activation:* We will apply linear mixed models with FFA as the outcome, OSA severity or SNS variables (e.g. AHI, ODI, arousal index, HR, urine catecholamines) as fixed factors and subject ID as the random effects variable. Iterative time lags will be used to account for potential delayed effects of dynamic variables. We hypothesize that plasma FFA level will be independently associated with AHI, arousals from sleep, HR elevation, or urine catecholamine level.
- *Identification of robust “responders”:* We will examine FFA elevation as a dichotomous outcome, defining “FFA responders” as those who exhibit Δ FFA $\geq 10\%$ during CPAP withdrawal (subject to change depending on the distribution of responses; the 10% threshold is based on a median increase in nocturnal FFA of $\sim 8.9\%$ in our preliminary data). OSA severity, sleep architecture, sex, age, and fat mass will be compared between responders and non-responders.
- *Identification of potential “downstream” effects of FFA elevation.* We will test the association between nocturnal FFA profile and other cardiometabolic outcomes (e.g. morning OGTT, endothelial function). Multivariable regression will be used to adjust for potential confounders such as age, sex, and BMI.
- *Identification of potential circulating genetic/epigenetic changes.* An exploratory aim of this study is to examine effects of CPAP withdrawal on peripheral blood mononuclear cell (PBMC) gene expression. We will utilize real-time polymerase chain reaction (RT-PCR) arrays (Qiagen MAP Kinase RT2 Profiler and Human Toll-Like Receptor (TLR) Signaling Pathway RT2 Profiler PCR Arrays, Qiagen, Valencia, CA) to characterize gene changes that result from nocturnal hypoxemia.

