Sample Size: One of the stated goals of this study is to examine sex-specific lipolytic responses to CPAP withdrawal. We base our sample size on the ability to detect a difference in FFA elevation between men and women. In the 20 non-diabetics of our preliminary data, the average Δ FFA during CPAP withdrawal was 0.047 ± 0.04 mmol/l in men (n=13), and 0.021 ± 0.04 mmol/l in women (n=7). This yields a medium effect size (Cohen's $d = 0.65$). To detect a sex difference at 80% power at a significance level of 0.05, requires a sample size of 78 (39 men and 39 women). We anticipate potential technical problems (e.g. IV failures, hemolysis, and poor sleep efficiency) leading to loss of 15% data. Therefore, our target enrollment will be 92 subjects.

Early stopping rule

At any point in the study, the subject may decline to participate. Indications for stopping are the development of severe adverse events. The DSMB and IRB will be informed of any adverse events. Any serious adverse events will result in study discontinuation.

7. Risks

- a. Medical risks, listing all procedures, their major and minor risks and expected frequency.

Venipuncture: May be associated with discomfort and bruising. Infection or irritation (phlebitis) can occur at the IV site.

Phlebotomy: In total, the blood collected will be approximately 174 cc (as compared to approximately 350 mL during a donation). Theoretically, if too much blood is lost, this could lead to low blood pressure and cardiovascular stress or dizziness.

Withdrawal of CPAP: During abstinence from CPAP over 3 days, subjects may experience relatively unrefreshing sleep. During the night, they may experience arousals from sleep, morning headache. During the daytime, they may experience subjective and/or objective daytime sleepiness. The risk of sleepiness contributing to an accident such as work-related injury or motor vehicle collision is also increased. Chronically, OSA is associated with increased risks of hypertension, diabetes, stroke, and ischemic heart disease. In a recent study on the effects of 2-weeks of CPAP withdrawal, there were modest and gradual increases in daytime blood pressure, heart rate, and triglycerides⁷. Risks of stopping CPAP for 2 weeks is therefore a low-risk, high yield research method. In this study, withholding CPAP for a few days is associated with even fewer risks.

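### The secondary tests of whether age, sex or BMI modify the FFA response to half-hourly OSA severity name no random slope; if response varies between people, their type I error exceeds 5%

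*Combined protocol and SAP*

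**What the plan says.** Section 4a, Data Analysis and Anticipated Outcomes, describes the repeated FFA analysis as a "mixed linear model analysis using condition as a fixed factor and subject ID as a random factor". The same paragraph adds a secondary analysis of patient-level (static) determinants of FFA "and whether these variables interact with sleep" variables, labelled dynamic, such as OSA severity. Sleep physiology is to be reduced to 30-minute bins to match the blood samples.

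Study Statistics, Specific Aim 2, gives the model for OSA severity and sympathetic variables. These enter "as fixed factors and subject ID as the random effects variable". Neither place mentions a random slope, a subject-by-night term, a within-subject covariance structure or a robust standard error.

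On the purpose of Aim 2, the section states: "These analyses are primarily designed to understand the heterogeneity of lipolysis during CPAP withdrawal". It also plans a separate subject-level sex comparison, "comparing mean change in FFA level during CPAP withdrawal between men and women (unpaired T-test", and a comparison of FFA responders with non-responders. The Sample Size paragraph reports preliminary ΔFFA of "0.047 ± 0.04 mmol/l in men (n=13), and 0.021 ± 0.04 mmol/l in women" (n=7).

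**The concern.** Age, sex and BMI take one value per person. Evidence that one of them changes the slope of FFA on OSA severity therefore comes from about 78 people, however many samples each person gives. A random intercept absorbs differences in FFA level only. Person-to-person differences in slope have no term of their own, so the interaction is judged against sample-level residual noise averaged over some 2,650 samples. The test can then reject because people differ, whether or not sex, age or BMI explains the difference.

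At stake is the error rate of the static-by-dynamic interactions. These are the planned tests of who responds more strongly to a given OSA severity, and a false modifier could misdirect follow-up work on susceptibility.

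**Working it through.** **Inputs from the documents.** SD of ΔFFA 0.04 mmol/l in each sex, means 0.047 and 0.021, 39 + 39 evaluable, 15% loss (Sample Size). Samples every 30 minutes from 10:30 PM to 6:30 AM, so 17 per night (Blood work and urine collection), over two nights: 78 × 2 × 17 = 2,652.

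**Inputs not in the documents (assumptions).** The within-night residual SD, σ, and the spread of OSA severity between people and between bins.

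**Step 1: the plan's own figure.** d = (0.047 − 0.021)/0.04 = 0.65. A two-sided t-test at 0.05 needs 38.14 per group for 80% power, so 39 + 39 = 78 (power 80.9%). Then 78/0.85 = 91.8, rounded up to 92. The stated numbers reproduce, and they confirm that 0.04 is used as an SD.

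**Step 2: room for true variation.** With independent residuals, noise alone gives SD(ΔFFA) = σ√(2/17). This equals 0.04 when σ = 0.04/√(2/17) = 0.117. Below that value there is room for true differences in response; at or above it there is none.

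**Step 3: closed form.** Treat severity as one value per night. The actual SD of a person's change is 0.04, but the intercept-only model works with σ√(2/17). Rejection of a true null is then 2[1 − Φ(1.96 × σ√(2/17)/0.04)].

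| σ (mmol/l) | σ√(2/17) | 1.96 × ratio | Rejection |
|---|---|---|---|
| 0.03 | 0.0103 | 0.504 | 61% |
| 0.05 | 0.0171 | 0.840 | 40% |
| 0.07 | 0.0240 | 1.176 | 24% |
| 0.08 | 0.0274 | 1.345 | 18% |
| 0.10 | 0.0343 | 1.681 | 9% |
| 0.117 | 0.0401 | 1.966 | 5% |

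**Step 4: simulation with half-hourly severity.** 78 people, 2 nights × 17 samples, no true modifier, 3,000 runs per setting. Severity was scaled to an average between-night difference of 1, with assumed between-person variance 0.1735. The slope SD τ was set so that total SD(ΔFFA) stays near 0.04: τ² = (0.0016 − 2σ²/17 − 0.038² × 0.1735)/1.1735, where 0.038 is the pooled mean, (13 × 0.047 + 7 × 0.021)/20.

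| σ | τ | Intercept only, sex | Intercept only, continuous factor | t-test on per-subject slopes |
|---|---|---|---|---|
| 0.03 | 0.0326 | 66% | 66% | 4.5% |
| 0.05 | 0.0300 | 51% | 51% | 4.6% |
| 0.08 | 0.0225 | 26% | 25% | 5.5% |
| 0.10 | 0.0121 | 10% | 9% | 5.2% |

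A second simulation (between-person AHI SD assumed 10/h, 1,500 runs) gave 11%, 31% and 47% at σ = 0.10, 0.07 and 0.05, with 5% to 6% for per-subject slopes. With no slope variation the intercept-only model held its level (4.5% to 5.6% in the first set, 5% in the second), which isolates the cause. A random-slope mixed model, in a near-identical setup with only 150 runs per setting, gave 5% to 7%.

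**Step 5: a subject-by-night term alone.** Taking mean AHI as 30/h off CPAP and 2/h on CPAP with Poisson half-hour counts (assumed), rejection after removing night effects was about 5% to 15%. Most of the contrast in severity lies between nights, so a night term absorbs much of the excess, but slope variation within nights remains.

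**The case against.** The strongest reply is that the plan never names the model for these interactions. The subject-ID model in section 4a is attached to the condition comparison, the Aim 2 mixed model lists no interaction, and naming subject ID as the random variable does not strictly exclude a random slope. This stands as a limit: the point is conditional on the usual reading. It does not remove the point, because no other random structure appears anywhere.

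A reader might infer that all of Aim 2, or the sample size, is compromised. The documents do not support that. The unpaired t-test of mean change by sex uses the person as the unit, as does the responder comparison, and the sample size rests on the former.

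A reader might also take the preliminary SDs as proof that slopes vary. They are not proof. The SD exceeds the mean in women (0.04 against 0.021) but not in men (0.04 against 0.047), and it mixes sampling noise and differing OSA severity with any true variation in response. The statement about heterogeneity is an aim, not a finding.

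Nor can a single inflation figure be given. At σ = 0.10, noise already takes 2 × 0.01/17 = 0.00118 of the variance of 0.0016, or 74%, so a true share of half or more is impossible there. At σ = 0.15, noise alone would give 0.051, above the reported 0.04.

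Finally, the analysis is secondary in a self-described pilot, and a subject-by-night term would cure much of the problem. Both are true; they limit the importance of the point without making the stated model valid for this test.

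**Conclusion.** The concern holds for the secondary static-by-dynamic interactions only. If those tests use a subject-ID random intercept and people differ in their FFA response, nominal 5% tests reject too often: about 10% at a residual SD of 0.10 mmol/l, about 25% to 35% at 0.07, and as high as about 66% at 0.03. These rates rest on an SD of ΔFFA near 0.04, about 17 independent-residual samples per night, and assumed values for the residual SD and the spread of severity. Serial correlation between samples was not simulated. If the residual SD is near 0.117, noise explains all of the 0.04 and there is no inflation. The problem is worth correcting before analysis; it does not threaten the primary sample size or the subject-level sex comparison.

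**What to change.** State the model for the interactions in section 4a and under Specific Aim 2. For each static-by-dynamic interaction, add a by-subject random slope for the dynamic variable concerned (AHI, ODI, arousal index or heart rate), together with a subject-by-night term. Alternatively, estimate each subject's slope of FFA on that variable and regress the slopes on age, sex and BMI. Either way, base the degrees of freedom on the number of subjects. Name the two-stage slopes in advance as the fallback if the random-slope model does not converge.

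The cost is a sentence or two of analysis-plan text, with no new data, visits or participants. The downside is wider intervals for these interactions.
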